### 7. OVERALL STUDY SETTINGS

The study site rural Mount Darwin district in Mashonaland Central Province in Zimbabwe (see picture below) – pregnant women have few means of reducing heat exposure during a heatwave, and even drinking water may be scarce [61]. Health facilities, poorly-built brick households and informal housing in urban slums offer little to no protection

against heat exposure and are frequently 4-6°C warmer indoors than outdoors [10, 25] In Zimbabwe, primary data collection for Stage 1 of the study will occur at Chitse Clinic, Dotito Rural Health Clinic and Mount Darwin Hospital. Including multiple facilities and contrasting sites allows for assessment of how 'interventions interact with context' [62] within and between sites, and increases the potential transferability of the findings. Primary data collection for Stage 2 of the study will be conducted at Chitse Clinic, Dotito Rural Health Clinic, and Mount Darwin Hospital, and may extend to other rural facilities within the district within the catchment areas of these three primary sites.

# 7.1. Objectives

- To observe and document the experiences and responses of pregnant women to heat in antenatal clinics and the first stage of labour in maternity settings.
- To track how women's experiences and coping practices relating to heat exposure change over the course of their pregnancies (in community and healthcare settings)
- To document the microclimates and temperature variations that pregnant and
  postpartum women encounter by measuring personal temperature, temperature in
  healthcare facilities and in households in addition to weather and satellite data, in
  relation to activity changes and sleep disturbance.

- To document preferences around intervention attributes among women and key stakeholders and identify potential implementation challenges.
- To capture systems' perspectives on heat exposure in community and healthcare settings, and practical considerations that may influence intervention selection and optimisation through interviews with policymakers, district and facility managers, healthcare workers, and community leaders.
- To model alternative building and nature-based solutions by conducting temperature
  and humidity monitoring at the participating health facilities and in 20-25 households
  using digital temperature and humidity sensors positioned in the interior, as well as
  using downscaled weather data and local weather stations.
- To co-design multi-level, multi-component interventions to reduce heat impacts on maternal and newborn health (MNH) in diverse contexts.
- To evaluate intervention feasibility, processes, scalability, pilot-effectiveness, and health and social outcomes –

### 8. METHODS

The HAPI intervention is developed over two-stages (see Figure 3). Stage-1 involved formative research, that I inform the co-design of the complex intervention, while Stage-2 will include refining and evaluating this complex intervention. This protocol describes the project activities for Stage-2. Stage-2 is included as an amendment of the main protocol, after refinement of the methodology and interventions identified from Stage-1. Stage-2 will also leverage data and outputs from the HIGH Horizons project [63], which is implementing selected heat-adaptation interventions for healthcare workers in maternity facilities in Mt Darwin District, and developing an Early Warning System for pregnant women, but has no behavioural or nature-based components, and does not target community settings, households, or policy actors. Funding for interventions and all other project activities will be ring-fenced between HIGH Horizons and HAPI.

The specific activities that were undertaken as formative research under Stage-1 of the protocol were described in detail in separate description not included in this version under the following sub-headings:

- 1. Sub-Study 1: Ethnographic participant observations
- 2. Sub-Study 2: In-depth interviews with pregnant women and temperature monitoring
- 3. Sub-Study 3: Key informant interviews
- 4. Sub-Study 4: Health facility and household thermal monitoring and performance simulations
- 5. Sub-Study 5: Co-design multi-level, multi-component interventions to reduce heat impacts on maternal and newborn health

# 9. STAGE-2: FEASIBILITY, SCALABILITY AND PILOT EFFECTIVENESS TESTING, INTERVENTION OPTIMISATION AND THEORY-BASED EVALUATION

Stage-2 involves evaluation of the complex intervention using three complementary research designs, including a Participatory Action-Research design, a quasi-experimental pre-post intervention design, and a cost-consequence modelling. These three designs will occur concurrently over a period of approximately 17 months. Stage-2 also leverages data and outputs from the HIGH Horizons project [63], which is implementing selected heat-adaptation interventions for healthcare workers in maternity facilities in Mt Darwin District, and developing an Early Warning System for pregnant women, and HCWs but has no behavioural or nature-based components, and does not target community settings, households, or policy actors. Funding for interventions and all other project activities will be ring-fenced between HIGH Horizons and HAPI. Specifically, in Stage 2, we will test the proposed interventions to assess their feasibility, scalability, pilot-effectiveness, and cost-consequence modelling.

### Our specific objectives are:

- Assess Feasibility: We will determine whether these interventions can be practically implemented and scaled up in the the study site
- Evaluate Intervention Mechanisms: We will closely monitor the implementation process to understand how and why these interventions work in these distinct contexts.
- Pilot effectiveness: We will implement the complex intervention, focusing on refining
  and evaluating them throughout the process. This includes assessing their
  effectiveness in improving maternal and newborn health outcomes, with a specific
  emphasis on heat adaptation.
- Cost- consequence: The cost-consequence modelling in HAPI will evaluate the
  economic feasibility of community-led heat adaptation and mitigation interventions in
  Zimbabwe. It will capture both financial costs (e.g., expenditure on goods, services,
  and volunteer time) and non-financial costs (e.g., donated goods). Using top-down and
  bottom-up costing approaches, the model will allocate costs to specific activities and
  sites, informed by comprehensive data including expenditures, time sheets, and M&E

- outputs. Additionally, baseline assessments and time-motion studies will ensure accuracy in cost allocation. This modelling will assess the economic impact and sustainability of the intervention, guiding decisions on scaling and resource allocation.
- Stage 2 is critical as it will guide our decisions on scaling these interventions, ensuring they are likely effective and sustainable in reducing heat impacts on MNH in both urban and rural settings

### 10. STAGE 2 STUDY DESIGN

We will employ three complementary research designs, including Action-research, a quasi-experimental pre-post intervention study, and cost-consequence to evaluate intervention feasibility, processes, scalability, pilot-effectiveness, and health and social outcomes (See Figure 8). The action rsearch will involve two 6 months cycles to further refine and optimise intervention implementation. Intervention refinement will include a co-design process, similar to that undertaken in Stage-1 (described in Section 4.5), but simplified and targeted at specific experts or stakeholders who will reflect on the findings of the action research activities and help decide on intervention refinements, if any.

Figure 4: Study Activities

HAPI project month	18	19	20	21	22	23	24	25	26	27	28	29	30	31	32	33	34
Intervention delivery	Τ							Im	pleme	entatio	n of o	omple	ex inte	rventi	on		
Action research (Activity 2.1)						Cycle 1: Observe, Reflect, Plan, Cycle 2: Observe, Reflect, Plan, Act Plan, Act											
Quasi-experimental pre-post cohorts (Activity 2.2)		Quasi-experimental study															
Participant enrolment	int	Pre- ervent	tion										int	Post- tervent			
Follow-up of enrolled participants		Pre-intervention Post-intervention															
Cost-consequences (Activity 2.3)							Costing and modelling										

### 11. QUASI-EXPERIMENTAL PRE-POST INTERVENTION STUDY.

We apply a quasi-experimental pre-post-intervention design to evaluate intervention feasibility, processes, scalability, pilot-effectiveness, and health and social outcomes. In Zimbabwe, 400 women attending antenatal clinics at weeks 26-30 weeks of gestation will be enrolled before and then during intervention (named 'post-intervention cohort') (total n=800), and assessed four-weekly during pregnancy at routine clinic visits, and subsequently at childbirth and postpartum (planned within 72 hours). Semi-structured questionnaires will be administered to collect data on socio-economic status, heat impacts, behaviours related to heat and hydration, access to safe water, heat-resistance of dwellings, indigenous coping strategies, preferences around intervention attributes, intervention rankings, critical uncertainties, costs of service access and intervention participation, and implementation challenges (See appendix 31) We will also conduct biomedical assessments (ultrasound, blood and urine samples), and screening of wellbeing and for mental health conditions. Additional data will be extracted from the patient-held antenatal cards and birth records. Outcomes in the pre-intervention cohort of women will be compared with women in the post-intervention cohort.

### 11.1.1. Study Setting and population

Pregnant women attending antenatal care at sites in Mt Darwin District facilities between 26-30 weeks gestation, followed up at labour, 72 hours postpartum and where not possible, this visit window will close at 10 days after childbirth.

### 11.1.2. Inclusion and exclusion criteria

### 11.1.3. Inclusion criteria

- Pregnant, between 26-30 weeks' gestation
- 16 years and older at the time of consent
- Intending to give birth in Mt Darwin District health facilities
- Not experiencing serious complications of pregnancy that have required hospitalisation
- Willing and able to provide written consent to participate in the study.

### 11.1.4. Exclusion criteria

 Women in the pre-intervention cohort will be excluded from the post-intervention quasi experimental cohort.

### 11.1.5. Sample Size

For the purposes of determining the required sample size, the primary pilot-effectiveness outcome is mild-moderate hypovolemic maternal dehydration during labour (urine specific gravity >1.015, measured by handheld optical refractometer, Sper Scientific portable clinical refractometer 300005 or similar). This reflects both hydration practices, and heat exposure (fluid loss through perspiration). We calculated the sample size to provide sufficient power for country-specific analyses; a pooling across countries may not be possible due to heterogeneity in intervention package and effectiveness. With about 800 women and 15% attrition, we will have >95% power to detect a 15% difference in the proportion of women with primary outcome between the pre- and post-intervention cohorts. In the before cohort, based on a literature review, we estimated 30-60% of women will have mild-moderate dehydration during labour (level varying by ambient temperature and season).

### 11.1.6. Participant sampling

*Pre- and post-intervention cohorts*: Consecutive eligible women in Mt Darwin District health facilities will be approached for recruitment. Consecutive recruitment minimises selection biases. We will enrol at least 5-10 women per day, with each cohort including up to 400 women (up to 400 pre-intervention and up to 400 post-intervention). Duration of total planned follow up time is about 2-4 months for each woman, assuming that most women complete pregnancy at around 40 weeks gestation. Routine clinical follow-up visits at antenatal clinic are generally at 20-, 26-, 30-, 34-, 36-, 38-, and 40-weeks during pregnancy (+/- 7 days), then during the first stage of labor, and again postpartum within 72 hours postpartum (window closes 10 days after delivery). Pre- and post-intervention cohort recruitment is spaced around 9-12 months apart and timed to coincide with the hot season.

### 11.1.7. Recruitment and enrolment

Pre- and Post-Intervention Cohorts: The study team will collaborate with facility staff to identify pregnant women attending ANC services between 20 and 28 weeks of gestation who meet the eligibility criteria. These women will be invited to enroll in the study at 26–30 weeks of gestation. HCWs will assist the study team in determining the suitability of women attending the facility for ANC services on recruitment days. Facility HCWs will also be invited to participate as co-researchers. They will seek permission from eligible women to allow either the HCW (if their schedule permits) or a member of the study team to approach them regarding the study.

If the women agree, recruiters or HCWs will meet with them in a private room within the facility, either after their ANC visit or while they await another service. During this meeting, the recruiters will verify eligibility, provide a brief overview of the study, and gauge their interest in participation. The contact and basic demographic details (name, surname, age, and area of residence) of interested women will be documented in a screening log.

Pregnant women who meet the eligibility criteria and express an interest in participating will be provided with a study-specific information sheet (Appendix 22 and Appendix 23), either individually or in a group setting. The informed consent process will ensure participants have a clear understanding of the study procedures and will include private discussions to address any questions before obtaining signed consent. The comprehensive informed consent process is detailed in Section 11.1.

Once consent is obtained, a participant enrollment log will be completed for each participant. Each participant will then be assigned a unique participant ID, which will serve as their identifier on all study-related materials.

### 11.1.8. Remuneration

Women will be re-imbursed USD10 per study visit attended, for her time, effort and inconvenience during the study visit. Remuneration will be provided at the end of each interview in cash.

#### 11.1.9. Data collection

Data collection will occur at enrolment (26-30 weeks), and at a 4-week antenatal care follow-up visit visit , at childbirth and within 72 hours postpartum. These visits coincide with the MoHCC Basic Antenatal Care Visit Schedule for pregnant women . Informed consent will be conducted on the day of enrolment, following procedures described above and in further detail in Section 31. Contact details including telephone numbers, alternate telephone numbers and home address will be collected and logged separately from the database that captures study information

The first interview will take place during the summer months (between November 2024 - February 2025) with follow-up interviews conducted over the remainder of the hotter season, as per the schedule below(figure 9). Ideally pre-intervention cohort visits will be conducted from November 2024 to May 2025 and post-intervention cohort visits will be conducted from November 2025 to May 2026.

All interviews will be carried out by a research staff member and HCWs trained in conducting interviews and collecting study biomarkers. Enrolment semi-structured questionnaires will be interviewer-administered via CAPI (computer assisted personal interviewing) using a study tablet computer to collect data variables such as demographics, socioeconomics, housing type, water and electricity access, heat-related knowledge, current impacts of heat, behaviors related to heat and hydration, housing characteristics, and knowledge and use of indigenous coping strategies. Follow-up visit interviewer-administered questionnaires will be shorter and focus on heat-related knowledge, current impacts of heat, behaviors related to heat and hydration, use of indigenous coping strategies, access to safe water with post-intervention

postpartum questionnaires also including questions on preferences around intervention attributes, intervention rankings, critical uncertainties, costs of service access and intervention participation, implementation challenges, and reflections on the process of participating in this study. Questionnaires and interviews will be conducted in the language of participants' choice (but restricted to languages spoken fluently by the interviewers in our team).

The results of any routine ultrasound if available and blood tests that have been done will be extracted from the Maternity Case Record (MCR). Additional data will be extracted from the patient-held antenatal cards and birth records, including antenatal visit dates; delivery date; information to determine gestational age; prior pregnancy history; use of medication and substances; comorbid conditions; laboratory and point-of-care test results; vaccine history; anthropometry; ultrasonography findings; maternal and newborn complications during labour and delivery; newborn clinical features; and congenital anomalies. Where necessary, data missing from the MCR may be supplemented with data captured from the birth register.

We will conduct urine specific gravity measurements at enrolment and follow-up visits. Screening for wellbeing (WHO-5 or EQ5, or similar) and for mental health (PSS-7 or EQDL-5 or similar) conditions will also be conducted.

Figure 5: Study procedures and data collected as part of the quasi-experimental pre-post intervention study (N=800 women: 400 in pre-intervention, 400 in post-intervention

	Pre-interver	ntion bio-behav procedures (N=800)	ioural study	Post-intervention bio-behavioural study procedures (N=800)					
Study procedure	Enrolment in antenatal clinic (24-28 weeks gestation)	Labour ward admission	Postpartum (<72 hours after childbirth)	Enrolment in antenatal clinic (24-28 weeks gestation)	Labour ward admission	Postpartum (<72 hours after childbirth)			
Informed consent	Х			Х					
Contact details	Х			X					
Questionnaire for women									
- Socioeconomics and risk factors	x			x					
- Housing type and water access	х			х					
- Birth plans and preparedness	Х			Х					
- Heat-related knowledge	Х		Х	Х		х			
- Heat-protective behaviours	Х		Х	X		Х			
- Hydration practices	X	Х	Х	Х	Х	Х			
- Wellbeing (ONS wellbeing assessment)	х		х	х		х			
- Birth experience			Х			х			
- Self-reported exposure to the intervention						х			
- Acceptability of intervention						х			
Temperature monitoring									
- Intermittent skin temperature monitoring		x	х		х	х			
- Continuous temperature monitoring (wearable devices in subset of women only)	х	х	x	х	х	х			

 
Continuous indoor temperature monitoring in dwellings and facilities
 
	x	x	x	х	x	x			

 
Weather station and remote sensing
 
	х	x	x	х	х	x			
Pregnancy and birth records of women									
- Clinical outcomes in women (composite) ^		х	х		х	х			
- Clinical outcomes in newborns (composite)^			х			х			
Biological urine sample									
- Urine specific gravity assessment (primary outcome)	х	х	х	х	х	х			

- Maternal composite clinical outcomes: 1 or more of the following obstetric emergencies, emergency Caesarean section, preeclampsia/eclampsia, antepartum or postpartum haemorrhage, sepsis.
- Newborn composite clinical outcomes, 1 or more of the following: stillbirth, preterm birth, low birth weight, APGAR score ≤6, neonatal admission

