#### 18.1.2. Data Analysis

Evaluation of complex interventions involves consideration of a wide range of outcomes. For purposes of sample size, the primary pilot-effectiveness outcome is mild-moderate hypovolemic maternal dehydration during labour (urine specific gravity >1.015, measured by handheld optical refractometer, Sper Scientific portable clinical refractometer 300005). This reflects hydration practices, and heat exposure (fluid loss through perspiration). Secondary outcomes include process indicators for interventions, heat strain, mental wellbeing, composite maternal-clinical outcomes (obstetric emergencies, emergency Caesarean section, pre-eclampsia/eclampsia, antepartum or postpartum haemorrhage, and sepsis) and composite infant clinical-outcomes (preterm birth, low birth weight, APGAR score ≤6, and neonatal admission). Household temperatures will be used to determine effectiveness of household level interventions.

Baseline survey data will be analysed descriptively using percentages and presented in tables and will be included in reports and publications as such. Survey baseline and follow-up data will be compared using Student's t test, Mann-Whitney U test and chi-square, as applicable. Analyses will be presented overall, and by site, facility, and pre-specified population subgroups (to identify high-risk groups). Binomial multivariable regression will compute risk differences between pre- and post-measures in the primary outcome, controlling for multihazard factors and changes in climate exposures over time, with fixed-effect clusters. If size or direction of effectiveness differs markedly between facilities, or sites then analysis may be restricted to facility- or site-level.

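### Death after live birth and maternal death are in neither clinical composite, and the protocol's two lists for the newborn composite disagree on stillbirth

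*Protocol*

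**What the plan says.** The footnote to Figure 5 in Section 11.1.9 defines the newborn composite: "Newborn composite clinical outcomes, 1 or more of the following: stillbirth, preterm birth, low birth weight, APGAR score ≤6, neonatal admission". The maternal composite in the same footnote requires at least one of a list that ends "emergency Caesarean section, preeclampsia/eclampsia, antepartum or postpartum haemorrhage, sepsis".

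Section 18.1.2 defines both again. The infant composite there has four components: "preterm birth, low birth weight, APGAR score ≤6, and neonatal admission". The maternal one is given as "composite maternal-clinical outcomes (obstetric emergencies, emergency Caesarean section, pre-eclampsia/eclampsia, antepartum or postpartum haemorrhage, and sepsis". Both belong to the secondary outcomes, in the sentence that opens "Secondary outcomes include process indicators for interventions, heat strain, mental wellbeing".

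Follow-up is set in Section 11.1.1: "72 hours postpartum and where not possible, this visit window will close at 10 days after childbirth". Sections 11 and 11.1.9 plan the postpartum visit within 72 hours, and Figure 5 and Table 1 place the newborn composite at that visit. The record-extraction list in Section 11.1.9 ends with "maternal and newborn complications during labour and delivery; newborn clinical features; and congenital anomalies" and does not name vital status.

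**The concern.** A composite of adverse outcomes should not rank a death above a survivable event. Here admission of a newborn is a component and death of a liveborn baby is not, so a baby who dies without meeting another component scores better than a baby admitted who recovers. The maternal list has the same gap for a death from a cause it does not name.

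Section 9 sets out to assess whether the package improves maternal and newborn health outcomes. If the lists are applied as they stand, the gravest results in that domain enter the pre-post comparison only when the mother or baby also happens to meet another component. The two newborn lists also differ on stillbirth, so an analyst cannot tell which definition governs.

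**Working it through.** **The plan's own figure.** The one power statement concerns the primary outcome, dehydration in labour, and this point does not depend on it. It reproduces. The number per cohort after 15% attrition is 400 × 0.85 = 340. Power = Φ{[d − 1.96·√(2p̄(1−p̄)/n)] / √([p₁(1−p₁) + p₂(1−p₂)]/n)} with n = 340 and d = 0.15. Alpha is not stated, so two-sided 0.05 is assumed, and the difference is read as 15 percentage points. Over baselines of 30-60%, power runs from 97.6% (57.5% to 42.5%) to 99.7% (30% to 15%), above the stated 95%.

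**The lists side by side.**

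| Event | Figure 5 footnote | Section 18.1.2 |
|---|---|---|
| Stillbirth | listed | not listed |
| Preterm birth, low birth weight, APGAR ≤6, neonatal admission | listed | listed |
| Death after live birth | not listed | not listed |
| Maternal death | not listed | not listed |

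**Is death an outcome elsewhere?** Mortality appears in the background (Sections 5.1.1 to 5.1.3). Section 33 mentions miscarriage and stillbirth, as a wellbeing matter for women in the serial interviews. The adverse-event examples in Section 25.1.2 are disclosure of sensitive information and loss of data. None of these is an outcome definition.

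**Applying the rule.**
- Liveborn at term, normal weight, APGAR 8, not admitted, dies within the observed period: 0 components, no event.
- Same baby, briefly admitted, survives: 1 component, event.
- Stillborn at term with normal weight: event under Figure 5. Under Section 18.1.2 it depends on whether an APGAR score is recorded for a stillborn baby, which the protocol does not say.

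**Size.** The documents give no mortality rates, so both inputs below are assumptions. Babies scored event-free = 340 × (proportion dying early) × (share of those meeting no listed component), taking one baby per woman.
- Low: 340 × 0.01 × 0.10 = 0.34, or 0.1 percentage points.
- Middle: 340 × 0.02 × 0.25 = 1.7, or 0.5 percentage points.
- High: 340 × 0.03 × 0.50 = 5.1, or 1.5 percentage points.

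A narrower assumption on the full 400 (1 to 2.5% dying, 10-40% uncaptured) gives 400 × 0.010 × 0.10 = 0.4 to 400 × 0.025 × 0.40 = 4. For mothers, assumed mortality of 0.1 to 0.5% gives 340 × 0.001 = 0.34 to 340 × 0.005 = 1.7 deaths per cohort, before removing those who already meet a listed component.

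**The case against.** A reader might infer that neither composite counts any death. The documents do not support that: the Figure 5 list includes stillbirth, which is a fetal death. Only the Section 18.1.2 version omits it.

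A reader might also picture a baby who goes home and dies on day 4. For a baby seen on schedule, that death falls after the planned 72-hour contact. Day 10 is a fallback for visits that could not be held in time. The death is then a limit of follow-up rather than a misclassification by the composite. The point therefore holds only for deaths inside the period actually observed.

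The maternal gap is narrower than it looks. Haemorrhage, eclampsia and sepsis are listed, and Section 18.1.2 has obstetric emergencies as an open, undefined component. (In the Figure 5 footnote the punctuation leaves it unclear whether those words are a component or a label for what follows.) Many maternal deaths would already qualify. Many babies who die early would likewise qualify through prematurity, low weight, low APGAR score or admission.

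It is tempting to add that deaths will be dropped as missing, or that the composites will favour the cohort with more deaths. The protocol says neither. How to handle a participant who dies before a visit is commonly left to an analysis plan, and no passage suggests that deaths differ between cohorts. Section 18.1.2 says only what the secondary outcomes include, so separate reporting of deaths is not ruled out, and Section 30 gives serious adverse events a route to the ethics committees.

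All of this limits the size and reach of the point. It does not remove it, because the protocol itself fixes the component lists, in two places, and an analysis plan that followed either would carry the omission forward.

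**Conclusion.** The point holds in a limited form. Death after live birth and maternal death are in neither version of the composites, and the two newborn lists contradict each other on stillbirth. Both findings rest on the text alone.

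The likely effect on the composite rates is small, about 0 to 5 babies per cohort. That range rests entirely on the assumed mortality and assumed share uncaptured, and a window closing at 72 hours would catch fewer deaths than one covering the whole early neonatal period. The composites are secondary outcomes, and the primary outcome and its power are untouched. At these counts the study could not show an effect on mortality even with corrected lists. The reason to change them is validity: a composite of harm should not score a death inside its own observation period as a good result. The correction is worth making but does not threaten the study's main conclusion.

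**What to change.** 1. Make Section 18.1.2 and the Figure 5 footnote agree, with stillbirth listed in both.
2. Add death after live birth to the newborn composite and maternal death from enrolment to the maternal composite. Close both at one fixed point, the same for every participant and both cohorts, for example 72 hours after birth to match the planned visit. An endpoint tied to the actual visit date would observe some pairs for about 3 days and others for up to 10, and could give unequal ascertainment between cohorts.
3. Count a known death in that window as an event.
4. Record vital status of mother and baby at the existing postpartum contact as well as from the case record and birth register. Facility records alone may miss deaths at home. Where the visit takes place before 72 hours have passed, status at 72 hours needs confirming; Section 32 already foresees telephone contact and home visits for some women.
5. Report deaths separately by cohort, including any learned of later up to day 10.

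The cost is protocol wording and one vital-status field per mother and baby, with a short confirmation for early visits. Composite rates rise slightly, and deaths after the fixed window are reported only descriptively.
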